9.6.1.5 Expected adverse events

For this study, the applicable reference document is the most current version of the investigator's brochure (IB) for neladenoson bialanate.

Overview listings of frequent events that have occurred so far in the clinical development are shown in the current IB. If relevant new safety information is identified, the information will be integrated into an update of the IB and distributed to all participating sites.

14 FEB 2017 Version: 1.0 Page: 53 of 85

The expectedness of AEs will be determined by the sponsor according to the applicable reference document and according to all local regulations.

9.6.1.6 Adverse events of special interest

Adverse events of special interest have to be reported to the sponsor along the timelines set for serious adverse events (even though they may not be classified as serious), i.e. within 24 hours of the investigator's awareness, as described in section 9.6.1.4.

Adverse events of special interest are:

- Symptomatic bradycardia (HR < 50 bpm)
- Findings in ECG and / or AVIVO device as follows:
 - o Mobitz type I AV-block leading to withdrawal or interruption of study drug
 - Mobitz type II AV block leading to withdrawal or interruption of study drug or leading to any change in therapy
 - o Third degree AV blocks

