3.4 Rationale of the study

The main limitations of using full A1R agonists in cardiovascular indications such as HF are undesired cardiac effects, such as bradycardia and higher degree AV block as well as negative cardiac inotropy and dromotropy. In contrast, preclinical data show that the partial adenosine A1R agonist neladenoson bialanate can be used to modulate and trigger primarily favorable pharmacological responses for HF therapy and avoid undesired effects such as AV conduction abnormalities and higher degree AV block. Nevertheless, based on the mode of action, there are theoretical concerns particularly with regard to undesired effects, such as bradycardia and higher degree AV block for an A1R agonist, which might be aggravated by concomitant use of heart rate decreasing drugs like β-blockers.

The purpose of this clinical trial is to assess the safety, tolerability and the pharmacokinetic and pharmacodynamic response of 20 weeks' treatment with neladenoson bialanate compared to placebo in patients with chronic HFpEF on appropriate therapy for specific co-morbidities and to find the optimal dose for a further Phase III trial.

4. Study objectives

The objective of the study is to find the optimal dose of neladenoson bialanate for the Phase III trial by detecting and characterizing a significant dose-response relationship in the primary efficacy endpoint, absolute change from baseline in 6-minute walking distance (6MWD) at 20 weeks, in patients with chronic heart failure with preserved ejection fraction (HFpEF), and by characterizing the safety, tolerability and pharmacodynamic effects of the compound when given in addition to appropriate therapy for specific co-morbidities.

An exploratory objective is to further assess pharmacokinetic parameters and blood and urine biomarkers.

For variables please see Section 10.3.1.

Considering the exploratory nature of phase II studies and the uncertainty around the most appropriate endpoints in HFpEF, the sponsor will take the totality of the data (including secondary / exploratory endpoints) into consideration regarding the benefit / risk assessment and the decision to move into phase III.

14 FEB 2017 Version: 1.0 Page: 22 of 85

5. Study design

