10.3.1.4 Safety variables

Safety and tolerability variables are:

- Adverse events (Section 9.6.1), including
 - SAEs, AEs, treatment-emergent AEs and AEs of special interest, including AV blocks > I°
 - SAEs and AEs leading to discontinuation of interruption of study drug, including AV blocks in particular
- Laboratory abnormalities (Section 9.6.3.1), measured values and change from baseline, in particular
 - o Change in renal function measured by eGFR change from baseline
 - Change in liver function measured by bilirubin (total and fractions), AST and ALT from baseline
- 12-ECG abnormalities (Section 9.6.3.3) and PR interval duration
- Blood pressure and heart rate (Section 9.6.3.4); measured values and change from baseline
- Number of clinically significant findings in ECG and / or AVIVO device report

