6.3.4 Adverse events

All adverse events (AEs) will be coded according to the Medical Dictionary for Regulatory Activities (MedDRA) in its latest version which is specified in the TS domain.

A treatment-emergent AE is defined as any event arising or worsening after the start of study drug administration until 6 weeks after the last study medication intake.

Summary statistics (frequency and percentage of subjects) will be presented by treatment group using MedDRA for the following:

- Incidence rate of treatment-emergent AEs.
- Incidence rate of drug-related treatment-emergent AEs.
- Incidence rate of treatment-emergent AEs leading to death.
- Incidence rate of treatment-emergent AEs leading to permanent withdrawal of medication.
- Incidence rate of treatment-emergent AEs leading to interruption of medication.
- Incidence rate of treatment-emergent serious adverse events (SAEs).
- Incidence rate of treatment-emergent drug-related SAEs.
- Incidence rate of adverse events of special interest:
 - Symptomatic bradycardia (HR < 50 bpm)
 - Findings in ECG and / or AVIVO device as follows:
 - Mobitz type I AV block leading to withdrawal or interruption of study drug
 - Mobitz type II AV block leading to withdrawal or interruption of study drug or leading to any change in therapy
 - Third degree AV blocks

Statistical Analysis Plan

Listing of treatment-emergent AEs leading to withdrawal: subject ID, investigator AE term, primary SOC / preferred term, start and stop date of study drug administration, start and stop date (relative days) of AE, treatment arm, related to study drug / protocol-required procedure (yes/no), serious (yes/no), intensity, outcome.

Listing of treatment-emergent SAEs: subject ID, investigator AE term, primary SOC / preferred term, worst grade, start and stop dates of study treatment, start and stop date of AE , treatment arm, drug related (yes/no), intensity, outcome, action taken.

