9.1 AVIVO device variable specification

In the following, we describe the variables which will be analyzed.

- **Activity**

Variable	Summary measure(s)	Unit	Length of intervals
activity duration	duration	seconds	1 hour
activity intensity	mean	mG	1 hour
activity intensity	mean, max	%	daily

- **Abnormal findings that trigger a notifiable report are defined as below**

Finding	Notification criteria
Ventricular fibrillation	always notified
ICD discharge	always notified
Ventricular Tachycardia	any rate and ≥ 10 beats
Wide complex Tachycardia	any rate and ≥ 10 beats
PVCs	never notified
Sinus Bradycardia	≤ 30 bpm
Sinus Tachycardia	≥ 180 bpm
Supraventricular tachycardia	≥ 150 bpm AND ≥ 30 sec
A. Fibrillation or A. flutter	≥ 150 bpm AND ≥ 30 sec
A. Fibrillation or A. flutter	≤ 30 bpm and ≥ 30 sec

Statistical Analysis Plan

Protocol No.: < BAY 1067197/17582 >

Page: 31 of 38

A. Fibrillation or A. flutter	when notification criteria are met
Pause	≥ 3.0 sec
AV block 2nd (Mobitz I)	≤ 50 bpm
AV block 2nd (Mobitz II)	always notified
Isolated 2nd degree AV block (2:1)	≤ 50 bpm
High degree AV block	always notified
3rd Degree AV block	always notified
Other	
Patient triggered Events	when notification criteria are met
Technicians discretion	any

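### The AV-block entries on the special-interest list depend partly on treatment action and omit high-degree and 2:1 block, and the SAP plans no single count of AV block above first degree across ECG and device

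*Protocol*

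**What the plan says.** Protocol 9.6.1.6 gives the AESI list and its consequence: "Adverse events of special interest have to be reported to the sponsor along the timelines set for serious adverse events", that is, within 24 hours even when the event is not serious. The list has symptomatic bradycardia with heart rate below 50 bpm, and three ECG or device findings:

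- "Mobitz type I AV-block leading to withdrawal or interruption of study drug"
- Mobitz II on the same condition or on any therapy change. SAP 6.3.4 repeats this as "Mobitz type II AV block leading to withdrawal or interruption of study drug or leading to any change in therapy"
- "Third degree AV blocks", with no condition

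Protocol 10.3.1.4 describes the first group of safety variables as "SAEs, AEs, treatment-emergent AEs and AEs of special interest, including AV blocks > I" (the numeral stands for first degree). SAP 6.3.3 says the same. Neither attaches a treatment condition.

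SAP 9.1 defines which device findings trigger a notification. It treats Mobitz I, Mobitz II, 2:1, high-degree and third-degree block as five separate findings.

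For the analysis, Protocol 10.3.2.4 plans a table of patients with AV block above first degree in its paragraph on ECG findings, and deals with AVIVO data in a separate sentence. SAP 6.3.7 specifies that table from AVIVO/HealthPatch data only.

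**The concern.** For Mobitz block, whether an event enters the AESI row depends on what the investigator did as well as on what happened to the patient. If management differs between sites or patients, the row mixes incidence with management. High-degree and 2:1 block are not named at all, and neither document says whether a site should report them under another heading.

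Two uses of the data are affected. One is the 24-hour route to the sponsor for non-serious events. The other is the comparison between doses: AV conduction is a safety question the protocol itself raises, and a reader will look for one row per dose that answers it.

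**Working it through.** No figure in the plan needs reproducing. The check sets the sections side by side.

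**Step 1. Map the device findings in SAP 9.1 onto the AESI list (Protocol 9.6.1.6, SAP 6.3.4).**

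| Block type in SAP 9.1 | Device notification | Status on the AESI list |
|---|---|---|
| Mobitz I | at or below 50 bpm | only if study drug is stopped or interrupted |
| Mobitz II | always | only if study drug is stopped or interrupted, or therapy is changed |
| 2:1 | at or below 50 bpm | not named |
| High degree | always | not named |
| Third degree | always | named, no condition |

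Tally: 1 unconditional + 2 conditional + 2 not named = 5.

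**Step 2. Compare the list with the safety variables.** Protocol 10.3.1.4 and SAP 6.3.3 have two consecutive bullets on adverse events. The first covers occurrence and mentions AV block above first degree. The second covers events that led to stopping or interrupting study drug, and again singles out AV block. The variables therefore keep occurrence and action apart, while the AESI list merges them for Mobitz block. This favours reading the first bullet as unconditional but does not prove it, because the clause on AV block follows four classes of event and may apply to all of them together.

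**Step 3. Follow one case.** AVIVO detects a high-degree block in a patient without symptoms. The event is not serious and study drug continues. The device service notifies it, and it enters the device table in SAP 6.3.7. On a plain reading of 9.6.1.6 it needs no 24-hour AESI report and does not enter the AESI row. The same holds for a non-serious Mobitz II block with no change to study drug or other therapy.

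**Step 4. Check whether another table gives the full count.** SAP 6.3.7 counts AV block above first degree from the devices. SAP 6.3.8 tabulates treatment-emergent 12-lead ECG abnormalities by treatment group, but specifies no count of AV block above first degree. The two sources also observe different days. Protocol Table 9—1 schedules 12-lead ECGs at baseline, Week 12 and Week 20, and 7-day AVIVO wear from Weeks -1, 0, 8 and 19. The Week 12 ECG lies outside every scheduled wear period, so a transient block seen only then cannot appear in the device table.

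**Step 5. Size.** The documents give no expected rate of AV block, so the number of affected events cannot be estimated. What can be stated is the weight of one uncounted patient, taking the planned group sizes in Protocol 10.4 as denominators:

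- 5 mg: 1/24 = 4.2 percentage points
- 10, 20, 30 or 40 mg: 1/48 = 2.1 percentage points
- placebo: 1/72 = 1.4 percentage points

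**The case against.** A reader might infer that the sections contradict each other outright. The documents do not support that. As Step 2 notes, the clause in 10.3.1.4 may only say that AV blocks are reported somewhere among the four classes of event. The wording is inconsistent or ambiguous, and no more.

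A reader might also infer that the plan misses the risk it names. That fails too. The words "avoid undesired effects such as AV conduction abnormalities and higher degree AV block" in Protocol 3.4 come from a sentence saying that preclinical data show the drug can do so. The next sentence raises bradycardia and higher-degree block as a theoretical concern. Symptomatic bradycardia and every third-degree block are AESIs whatever action is taken.

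Other capture is substantial:

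- All adverse events are recorded (9.6.1.3), and clinically relevant 12-lead abnormalities become AEs or SAEs (9.6.3.3). Treatment-emergent AEs are tabulated by MedDRA term and treatment group.
- SAP 6.3.7 and 6.3.8 tabulate device and ECG findings, and SAP 6.3.7 lists patients with significant findings.
- Serious events, including those the investigator judges medically important, have their own 24-hour route. An unblinded Data Monitoring Committee reviews safety.

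Nor can it be said that 2:1 and high-degree block never count. With symptoms and a heart rate below 50 bpm, either could qualify as symptomatic bradycardia. An investigator might also record one as Mobitz I or II, since SAP 9.1 sets device labels, not adverse-event terms, and no rule links the two.

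Finally, where to set the AESI threshold is the sponsor's choice. Widening only the SAP row would label as AESIs events that sites were never told to report as such.

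All of this stands and narrows the point. It does not make the AESI row independent of management, settle where the two unnamed types belong, or supply one count across both sources.

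**Conclusion.** The point holds in limited form. The AESI list is narrower than the safety variables suggest, conditions two block types on treatment action and leaves two unnamed. Three things follow:

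1. Non-serious blocks outside the listed conditions have no 24-hour AESI report.
2. The AESI incidence row by treatment group is not a measure of how often AV block above first degree occurred.
3. The SAP specifies no single count of such block across 12-lead ECG and device, although the protocol places that table under ECG findings.

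A dose effect confined to 2:1 or high-degree block could be absent from the AESI row, but it could still show in the device, ECG or AE tables. The conclusion assumes that sites apply the list as written and do not reclassify the unnamed types under a listed term; the documents neither require nor forbid that. With no rate given, the consequence for the dose comparison cannot be quantified beyond the per-patient weights shown. The change is worth making because it is cheap and uses data already collected. Which AESI definition is right is not decided here.

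**What to change.** Reconcile Protocol 9.6.1.6 and SAP 6.3.4 with Protocol 10.3.1.4 and SAP 6.3.3, changing both documents together so that sites and tables use one definition. State explicitly where high-degree and 2:1 block are reported and counted, whichever threshold the sponsor keeps.

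In the SAP, add a row by treatment group for patients with any AV block above first degree, from 12-lead ECG or device, broken down by the SAP 9.1 types and regardless of action taken. Show as a sub-row those followed by stopping or interrupting study drug or by a therapy change. Keep this row distinct from the AESI row unless the protocol list is amended to match.

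The cost is one extra table row and its programming. If the sponsor widens the AESI list, sites will also make a few more 24-hour reports.

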9.6.2 Pregnancies

Females of childbearing potential are excluded from the study. However, the investigator must report to the sponsor any pregnancy occurring in a female study patient during her participation in this study. The outcome of the pregnancy should be followed up carefully, and any outcome of the mother and the child at delivery should be reported.

The child's health should be evaluated at birth.

For a pregnancy in the partner of a male study patient, all efforts will be made to obtain similar information on course and outcome, subject to the partner's consent.

For all reports, the forms provided are to be used. The investigator should submit them within the same timelines as an SAE.

9.6.3 Further safety

9.6.3.1 Laboratory evaluations

All laboratory evaluations will be done by central laboratory. Additional re-tests for liver monitoring (Section 9.6.3.6) will be done locally.

Hematology: erythrocytes, hemoglobin, hematocrit, MCV, MCH, MCHC, reticulocytes, leukocytes, differential blood count, platelets

Clinical chemistry: aspartate aminotransferase (AST), alanine aminotransferase (ALT), alkaline phosphatase (AP), gamma glutamyl transpeptidase (GGT), lactate dehydrogenase (LDH), creatine kinase (CK), amylase, lipase, glucose, cholesterol (HDL, LDL, total), triglycerides, creatinine, urea, uric acid, bilirubin, total protein, albumin, sodium, potassium, calcium, chloride, magnesium, anorganic phosphate

Coagulation: partial thromboplastin time (PTT), international normalized ratio (INR)

14 FEB 2017 Version: 1.0 Page: 54 of 85

9.6.3.2 Physical examination

The physical examination (by means of inspection, palpation, auscultation) will be performed by a physician at the investigational site covering at least the organs of the cardiovascular, respiratory, abdominal and neurological system.

Abnormal physical examination findings are recorded either as medical history or as adverse events (see Section 9.6.1.1).

9.6.3.3 12-lead ECG

The standard 12-lead ECG will be evaluated by the investigator and the following parameters will be recorded in the eCRF: HR, PR interval, QRSD interval, QT interval (uncorrected). QTcB (QT interval frequency-corrected according to Bazett's formula) will also be calculated but will not be valid for evaluation. The frequency-corrected QT interval will be calculated by data management according to the formulas of both Bazett and Fridericia.

All ECGs recorded during the study will be evaluated by a physician. He / she will document the diagnosis(es) including an overall assessment of the findings and their clinical relevance. Any clinically relevant abnormality will be documented as an AE or SAE.

9.6.3.4 Blood pressure and heart rate

Heart rate and blood pressure (systolic and diastolic) will be measured by a member of the investigator's study team with the patient at rest.

9.6.3.5 **AVIVO monitoring**

AVIVO Mobile Patient Management System will be used to monitor patients' cardiovascular status as part of the safety assessment. The cardiac monitoring device will be worn as specified in Section 9.1.

The system is intended to continuously measure, record and periodically transmit ECG data. The system can detect (but is not limited to) higher degree AV-blocks > I°, SVTs (e.g. atrial fibrillation [AF], atrial flutter, paroxysmal SVTs), ventricular ectopy, bradyarrhythmias, conduction disorders and heart rate variability. Included in the service is the monitoring center - an independent certified diagnostic testing center staffed with ECG-trained technicians who read through the transmitted events 24h/7d. An electrophysiologist is also on staff for interpretation of difficult rhythms. The system has achieved CE mark and has US FDA clearance.

AF will be assessed as subclinical AF and AF burden as an exploratory endpoint. No patient symptoms will be captured as part of this analysis, if not reported by the patient at routine visits.

Apart from safety assessments, also the patient's everyday physical activity (e.g. duration, intensity) will be tracked by the AVIVO device. This is part of the secondary efficacy variables. Details of the cardiac monitoring and the device to be worn by the patient will be outlined in a manual that will be provided to all participating centers. All collected variables will be described in the SAP.

14 FEB 2017 Version: 1.0 Page: 55 of 85

9.6.3.6 Liver function monitoring

Any patient with an ALT or AST > 3 x ULN or alkaline phosphatase (AP) > 2 x ULN must be re-tested as soon as possible but at the latest within 48-72 hours of the investigator becoming aware of the result. This re-testing and any subsequent testing based on elevated levels should include measurement of ALT, AST, total and direct bilirubin, and AP, and will be assessed by local laboratory. Every effort should be made to clarify the etiology of elevated levels. Patient management is at the discretion of the investigator but the treating physician may continue the study drug during retesting. Liver function test monitoring should be performed as above for all patients even if the study drug is interrupted until tested values have normalized or returned to patient's baseline. If close liver monitoring is not possible then the patient should discontinue study medication.

For ALT or AST > 3 x ULN concurrent with a total bilirubin > 2 x ULN, every effort should be made to clarify any possible underlying disease(s).

The frequency of liver function tests based on re-test values is shown in Table 9—3.

Table 9—3: Liver function monitoring

ALT, AST or AP level at re-test	Frequency	Further notice
ALT or AST > 3 x ULN	2-3 times a week	Obtain details on liver related symptoms and exclude other causes of liver enzyme elevations
ALT or AST ≤ 3 x ULN	Once a week	Until return to normal or patient baseline levels
AP > 2 x ULN	2-3 times a week	Obtain details on liver related symptoms and exclude other causes of liver enzyme elevations

ALT = alanine aminotransferase; AP = alkaline phosphatase; AST = aspartate aminotransferase; ULN = upper limit of normal

Discontinuation of treatment should be considered if:

- ALT or AST > 8 x ULN
- ALT or AST > 5 x ULN for more than 2 weeks
- ALT or AST > 3 x ULN and (total bilirubin > 2 x ULN or INR > 1.5)
- ALT or AST > 3 x ULN with the appearance of fatigue, nausea, vomiting, right upper quadrant pain or tenderness, fever, rash, and / or eosinophilia (> 5%)
- AP > 2 x ULN or ALT/AP < 2 for more than 2 weeks if other causes of cholestasis are excluded

9.7 Other procedures and variables

Not applicable.

9.8 Appropriateness of procedures / measurements

All parameters, as well as the methods to measure them, are standard variables / methods in clinical studies and / or clinical practice. They are widely used and generally recognized as reliable, accurate, and relevant.

14 FEB 2017 Version: 1.0 Page: 56 of 85

10. Statistical methods and determination of sample size

10.1 General considerations

Statistical analyses will be performed by or under the supervision of the sponsor's study statistician and the assigned study statistical analyst using statistical analysis system (SAS); the version used will be specified in the SAP.

A general description of the statistical methods to be used to analyze efficacy and safety in this is study is outlined below. A detailed SAP will be provided as a separate document that will be finalized and approved before database lock. The SAP will accommodate protocol amendments or unexpected issues in study execution or data that affect planned analyses and will provide more details on the analytical approaches, output tables and figures.

A meta-analysis of this study (17582) and of the study 15128 in patients with HFrEF, which is conducted at the same time, will be specified in a separate SAP.

